### Main study endpoints:

Primary endpoint:

- Variability of mitoPO2 before and after red cell transfusion. This will be compared to traditional parameters used to measure tissue oxygenation and oxygen balance

Secondary endpoints:

- Association of mitoPO2 with (ischemic) organ damage
- Association of mitoPO2 with the microcirculation
- Duration of mechanical ventilation
- Need for continuous renal replacement therapy (CRRT)
- Length of ICU-stay
- Length of hospital-stay
- ICU-mortality
- 90-day mortality

**Study procedure:** Included patients will undergo red cell transfusion as planned. However, red cell transfusion will be delayed for 2 hours. At multiple predefined moments, before and after red cell transfusion, data collection including blood samples and measurements of mitoPO2 will take place. It will be directly processed.

**Nature and extent of the burden and risks associated with participation, benefit and group relatedness:** The risks are moderate in this study with no SAE known. The burden for the ICU-patients is moderate since it's a non-invasive measurement. The normal clinical practice will continue and will not be altered. Since most ICU-patients have in this very controlled environment a central venous catheter and arterial catheter in situ, they are the most ideal patients to investigate mitoPO2 feasibility, accuracy and associations with other physiological parameters.

---

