In this study, the mitoPO2 of the skin will be measured. Reliable measurements can only take place with sufficient concentrations of protoporphyrin IX in the mitochondria. Therefore, a self-adhesive patch containing 8mg of ALA (Alacare®; Spirig AG, Egerkingen, Switzerland) will be placed on the anterior chest wall for induction of PpIX, for at least 4 hours before the first measurement can take place. To enhance ALA penetration, the skin will be rubbed with alcohol to remove the exposed layers of stratum corneum. Hair, if present, will be shaved. Following at least 4 hours induction of PpIX, the ALA patch will be removed after the outline of the ALA patch is marked. To create steady and reliable

measurements, a specially designed plaster will be used to attach the COMET Skin Sensor (COMET Skin Sensor, Photonics Healthcare, the Netherland) to the skin. This plaster is referred to as the Skin Pad, it is not CE marked, and is adhesive on both sides. One side of the plaster is a silicon skin friendly side and the other a strong acrylic adhesive to which the Skin Sensor is attached.

Figure 2: Skin Pad

After placing the skin sensor, calibration measurements will be made to ensure the quality of the measurements. Thereto, 5 measurements will be made in the first minute to establish a reliable and stable measurement. Occlusion of the microcirculation will be accomplished via local pressure with the measurement probe, which we use to validate the actual mitoPO2 measurement. After these measurements, mitoPO2 will be measured each minute for 5 minutes to obtain a mean mitoPO2. To ensure that no other variables influence the measurements, measurement characteristics will be logged. In this log, the circumstances in which each measurement is made will be documented. Known intervening variables include, for example, skin temperature, thus skin temperature will be recorded. Other variables recorded in the log will be vasopressor use, dosage of the vasopressor, and nurse actions. Following mitoPO2 measurement, the ALA patch will be re-used to protect the exposed skin for phototoxicity until the next measurement. After completion of the mitoPO2 measurements the exposed skin will be protected from sunlight for 24 hours. An overview of the mitoPO2 measurement is given below.

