## 5. Methods

### 5.1 Study procedures

#### 5.1.1 General

Since research has shown that approximately 10% of critically ill patients can make autonomous decision regarding research participation, most decisions will be made by their substitute decision makers, who are already overwhelmed by the medical information of the patient itself. Furthermore, studies have shown that obtaining contact with their substitute decision makers can be difficult in 7%, no decision maker exist in 6% of the cases. In addition, approximately half of the opportunities to recruit patients are missed because of workload and narrow time windows for inclusion. Difficulties in recruitment of eligible patient can lead to delayed identification of (in)effective treatment/diagnostics and limitation of generalizability. Alternative consent models are therefore needed to improve recruitment and minimize withdrawal. Therefore, we will first ask all ICU patients admitted to the ICU, or their legal representatives, expected to stay at the ICU for longer than 24 hours for participation in our study. Patients admitted to the cardiothoracic department which will be admitted to the ICU post-operatively, will be asked for an informed consent on the day before the cardiothoracic operation. An information leaflet will be given and informed consent will be sought. Patients or their legal representatives will be told that a person can only participate in the study if he/she meets the inclusion criteria. However, if no legal representative could have been reached in person for written informed consent, while the patient meet the eligibility criteria, the patient will be included in the study and deferred informed consent will be sought within 48 hours after oral consent has been given. If written informed consent is available or oral consent given, at the moment the decision is made to administer a red cell transfusion, the self-adhesive ALA-patch will be placed. Due to logistics, the normal time elapsing between the decision of a non-emergency red cell transfusion and the actual administration is 2 to 3 hours. The induction time of PpIX is at least 4 hours, therefore red cell transfusion will be delayed by 1 to 2 hours. At no time red cell transfusion will be delayed in order to have enough time to induce PpIX if the patient is clinically in need of a red cell transfusion. To ensure this, the clinician responsible for the patient, and not the researcher, has the final decision in the timing of the red cell transfusion.

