### 5.3.4 Sample handling and Measurements:

Samples will be collected from

- central venous catheter (if applicable)
- arterial catheter

In order to make comparisons between different compartments of the body, blood samples (arterial, central venous) and cutaneous samples will be collected at predefined moments.

These moments during the pilot study are:

- Before transfusion (=T0)
- At the end of each transfusion (=T1)
- 30 minutes after T1 (=T2)
- 60 minutes after T1 (=T3)
- 180 minutes after T1 (=T4)
- 24 hours after T1 (=T5)

With the help of the pilot study, an overview of the measurements and parameters were made.

With the help of this overview, decisions were made regarding the number of measurement moments (e.g. no need for measurement 15 minutes after red cell transfusion). Details about which parameters are determined at each time point during this pilot study are described in appendix 2. For the laboratorial measurements a total of 42ml of blood will be taken (10ml at T0 and T5, 4ml at T1 and T2, 6ml at T3 and 7.5ml at T4). As can be seen in appendix 2, most of the measurements are part of standard care which minimalizes the burden for the patient.

Figure3: Measurement MitoPO2 with the Comet

Analysis of red blood cell transfusion on the intensive care unit at LUMC showed 69% of transfusions occurred during daytime (between 8.00hr and 18hr). The remaining transfusions were evenly distributed in the evening and night time. Since transfusions outside the normal daytime are mostly because of urgent medical reasons, no measurements will be done in the evening or night.

Besides time of transfusion, analysis of previous ICU data showed that the mean duration elapsing between the decision of a non-emergency red cell transfusion and the start of the transfusion is 2-3 hours. Thus, maximum of 2 hours delay for start of transfusion during this study is achieved. However, at no time red cell transfusion will be delayed if the patient is clinically in need of a transfusion in order to have enough time to induce PpIX. To ensure this, the clinician responsible for the patient, and not the researcher, has the final decision in the timing of the red cell transfusion. The delay of transfusion will be recorded to gain an insight in delay of transfusion.

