However, if the patient or legal representative could not have been reached in time for written informed consent, while the patient met the eligibility criteria, patient will be included with deferred consent procedure. Informed consent will be sought within 48 hours after inclusion of the patient. Deferred consent is therefore only used in situations where it is not possible to ask informed consent, including the following: lack of decision-making capacity of the patient due to illness severity, delirium, use of sedatives, analgesics and life-sustaining treatments; inability to contact the legal representative; overwhelming nature of medical information for the legal representative therefore influencing the capability of informed decision-making. At the moment the decision is made to administer a red cell transfusion, the self-adhesive ALA-patch will be placed, if the patient meet the eligibility criteria, and data collection for the study started. Due to logistics, the normal time elapsing between the decision of a non-emergency red cell transfusion and the actual administration is 2 to 3 hours. Therefore, the maximal delay of a non-emergency transfusion will be 1 to 2 hours. To ensure improper delay of red cell transfusion due to the study, the clinician responsible for the patient, and not the researcher, has the final decision in the timing of the red cell transfusion.

If written informed consent was given, but retracted by legal representative or patient after participation, the patient will be excluded and data will no longer be used. If patient or legal representative denies participation during the study, data collected until that time point will be used in the analysis. No further data will be collected.

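### The 2-hour maximum transfusion delay in Protocol 5.3.4 is derived from a mean wait and a minimum induction time, so it is an expected delay and not an upper bound; four sections label it differently

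*Protocol*

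**What the plan says.** Section 5.3.4 reports from earlier ICU data that "the mean duration elapsing between the decision of a non-emergency red cell transfusion and the start of the transfusion is 2-3 hours", and concludes in the next sentence: "Thus, maximum of 2 hours delay for start of transfusion during this study is achieved".

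The other term of the subtraction is in section 5.1.1: "The induction time of PpIX is at least 4 hours, therefore red cell transfusion will be delayed by 1 to 2 hours". There the 2-3 hours is called normal, not a mean: "the normal time elapsing between the decision of a non-emergency red cell transfusion and the actual administration is 2 to 3 hours". The patch goes on when the transfusion decision is made, so induction and the usual wait start together. Section 4 confirms that the induction time is a minimum; the patch stays on "for at least 4 hours before the first measurement can take place".

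The delay is also stated in two other places:

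- Summary, study procedure: "However, red cell transfusion will be delayed for 2 hours". The paragraph on burden and risks that follows adds: "The normal clinical practice will continue and will not be altered".
- Section 8.2: "Therefore, the maximal delay of a non-emergency transfusion will be 1 to 2 hours".

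Sections 5.1.1 and 5.3.4 also say that transfusion is not held back for induction in a patient who clinically needs it, and that the treating clinician decides the timing. Section 5.3.4 has the delay recorded, and section 5.4.2 lists it among the safety outcomes.

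**The concern.** A maximum needs the shortest usual wait and the longest induction. The protocol uses an average wait and the shortest induction, and then calls the result a maximum. Both substitutions make the delay look shorter than a true upper bound would.

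The delay is a change that the study makes to the timing of care in critically ill patients, and it is a declared safety outcome. If 2 hours stands as a maximum, observed delays will be read against a ceiling that the protocol's own figures do not support, and longer delays will look like departures from plan when the design allows them. The differing labels add to this, because a reader cannot tell whether 2 hours is what every patient gets, what is typical, or the most that can happen.

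**Working it through.** **Inputs from the protocol**

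- Usual wait W from decision to start: 2-3 h, called a mean in 5.3.4 and normal in 5.1.1 and 8.2. No standard deviation, percentile or range of individual waits is given.
- Induction time I: at least 4 h (sections 4 and 5.1.1), counted from the transfusion decision. No upper limit is given.
- T0 measurement M, made after induction and before transfusion: about 1 minute of calibration plus 5 minutes of measurement (section 4), so about 6/60 = 0.1 h.

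**Step 1: reproduce the protocol's figure.** Delay = I − W, with I = 4 h:

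- W = 3 h: 4 − 3 = 1 h
- W = 2 h: 4 − 2 = 2 h

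This returns the 1-2 hours of 5.1.1 and the 2 hours of 5.3.4. The subtraction is correct. What it yields is the expected delay for a typical wait at the shortest permitted induction.

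**Step 2: check whether 2 h bounds the individual delay.** For a patient who completes induction, delay = I + M − W.

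| Induction I | M | Usual wait W | Delay |
|---|---|---|---|
| 4 h | 0 | 1.5 h | 2.5 h |
| 4 h | 0 | 1 h | 3.0 h |
| 4 h | 0.1 h | 2 h | 2.1 h |
| 4.5 h | 0 | 2 h | 2.5 h |

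Waits of 1 and 1.5 h and an induction of 4.5 h are illustrations, not figures from the protocol. The third row uses only the protocol's own numbers and already passes 2 h slightly. A bound of 2 h holds only if no individual wait is under 2 h, induction is exactly 4 h and the T0 measurement takes no time.

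**Step 3: size, as an illustration only.** At exactly 4 h of induction and with M = 0, delay exceeds 2 h when W < 2 h. Assume a gamma-distributed wait with shape (mean/SD)² and scale SD²/mean. P(W < 2 h) is then:

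| Mean wait | SD 0.5 h | SD 1.0 h | SD 1.5 h |
|---|---|---|---|
| 2 h | 53% | 57% | 60% |
| 2.5 h | 16% | 34% | 44% |
| 3 h | 1.3% | 15% | 28% |

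Normal and lognormal waits over the same grid give about 1% to 63%. The distribution and every SD are assumptions, and the clinician's override is ignored. The width of the range shows only that the protocol's figures do not settle the share.

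**Step 4: compare the four statements.**

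| Place | Figure | Kind of quantity |
|---|---|---|
| Summary | 2 h | fixed |
| 5.1.1 | 1-2 h | expected |
| 5.3.4 | 2 h | maximum |
| 8.2 | 1-2 h | maximum, given as a range |

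The top figure is the same throughout; the kind of quantity is not. The Summary's statement that practice is unaltered also conflicts with the delay it has just announced.

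**The case against.** The strongest reply is that nothing is miscalculated. Four hours minus 2-3 hours is 1-2 hours, all four passages share 2 hours as the top figure, and the fault comes down to one word. If 2-3 hours is read as the usual range, as the word normal in 5.1.1 and 8.2 allows, then 2 hours is the top of the planned delay at 4 hours of induction. This stands as far as the arithmetic goes. It does not rescue the maximum: 5.3.4 calls the wait a mean, a usual range is not the full range, and induction is still only bounded from below.

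The second reply is that patients are not protected by the 2-hour figure. Emergency transfusions are excluded, transfusion is not held back in a patient who needs it, and the clinician decides the timing. That stands too. A reader might infer that every patient whose usual wait is under 2 hours will be delayed by more than 2 hours; the override means that the documents do not support this. The override sets no numerical limit, however, and 5.3.4 derives its maximum from the mean wait, not from the override.

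A reader might also infer that the study's moderate risk rating rests on the delay. The documents do not say so. The Summary and sections 7.2, 7.8 and 10 base the assessment on the non-invasive measurement, the ALA patch and the light load.

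Finally, the 1-2 hours should not simply be renamed the average delay. With induction of at least 4 hours it is a lower bound on the average among patients who complete induction, while the override may lower the average over all patients.

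**Conclusion.** The point holds as one of labelling and consistency. The 2-hour figure reproduces, but as an expected delay at the minimum induction time for a typical wait. Calling it a maximum claims a property that the design does not have. Delays above 2 hours are possible for patients who complete induction and would otherwise have waited under 2 hours, or whose induction plus T0 measurement takes more than 4 hours when the usual wait is about 2 hours.

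How often this would happen cannot be derived from the protocol. The 1% to 60% range rests wholly on assumed spreads and leaves out the clinician's override, so it is no estimate of actual delays. The primary endpoint, the sample size and the analysis are not affected. What is affected is the description of a study-imposed delay and the yardstick for a listed safety outcome.

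**What to change.** - Reconcile the Summary and sections 5.1.1, 5.3.4 and 8.2 so that they describe the same kind of quantity.
- Describe 1-2 hours as the expected delay at the minimum 4-hour induction for a typical usual wait, subject to the clinician's decision on timing, and not as a maximum.
- Correct the Summary's statement that normal practice is unaltered, so that it agrees with the delay stated there.
- From the ICU data already analysed, give the spread of usual decision-to-start times or the share under 2 hours, if available. The recorded delay can then be read against what the design implies.

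The cost is wording in four places, plus one short summary if the earlier data can still be drawn on. The stated figure becomes less favourable. Which delay is acceptable is for the clinicians and the ethics committee.

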### 5.3.5 Other measurements

Also, cardiac output will be measured continuously by limited invasive methods such as the Vigileo/FloTrac. This measurement is done with the help of an already placed arterial catheter. VO2, DO2 and oxygen extraction ratio will be calculated.

Sublingual side stream dark field imaging is the only non-invasive validated instrument to evaluate the microvascular perfusion in critical ill patients. It will be used during this study to assess the microcirculation before and after red cell transfusion and compare this with the mitoPO2 measurements.

## 5.4 Study parameters

### 5.4.1 Main study outcomes

The primary endpoint is the change of mitoPO2 before and after red cell transfusion. This will be compared to change in traditional parameters used to measure oxygenation and oxygen balance (ScvO2, SaO2, PaO2, PvO2, CI, and lactate).

### 5.4.2 Secondary outcomes

Secondary study outcomes include:

- Value of mitoPO2 measurements in predicting (ischemic) organ damage. The following parameters for organ damage (that are routinely collected) will be assessed: lung (pO2/FiO2 ratio), heart (troponin, CK, an ECG, CI), renal (creatinine, urine production, glomerular filtration rate, RIFLE classification), brain (delirium, RASS) and SOFA score. More details about the timing of these parameters are given in appendix 2.
- Microcirculatory value of mitoPO2
- Duration of mechanical ventilation
- Need for renal replacements therapy
- Length of ICU stay
- Length of stay in hospital
- Hospital mortality
- ICU mortality
- 90-day mortality
- Assessment the safety of mitoPO2 measurements
  - Delay of transfusion because of mitoPO2 measurements
  - Adverse and serious adverse events of the mitoPO2 measurements

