### 2.2 Endpoints

In this phase 1 diagnostic study we aim to investigate mitoPO2 test's feasibility, accuracy, and associations with other physiological parameters of oxygen balance and tissue oxygenation and with ischemic organ damage in critically ill patients with anaemia.

Specific objectives:

1. To determine the feasibility and variability of mitoPO2 measurement in critically ill ICU patients before and after a red cell transfusion.
2. To describe the effects of red cell transfusion and the associated change in Hb on mitoPO2 and on other physiologic measures of tissue oxygenation and oxygen balance such as, arterial oxygen saturation, central venous oxygen saturation (ScvO2, measured in either the jugular or subclavian vein, if applicable), lactate, and DO2 minus VO2 (difference between oxygen consumption and delivery).
3. To describe the association between mitoPO2 and vital organ functions, as assessed by SOFA (Sepsis related Organ Failure Assessment) score, duration of mechanical ventilation, duration of vasopressor therapy, myocardial ischemia, serum creatinine, RIFLE classification for renal function, need for renal replacement therapy, Glasgow coma score, RASS, ICDSC score.
4. To describe the association between mitoPO2 measurements and the microcirculation

With this in mind, we will assess the following parameters:

1. Prognostic: duration of mechanical ventilation, need for renal replacement therapy, ICU-stay, hospital stay, ICU-mortality, 90-day mortality, measurements of ischemic damage (particular in patients following transfusion).
2. Etiologic: levels and time course of markers of ischemia-reperfusion in relation to the clinical course (such as duration of mechanical ventilation, need for renal replacement therapy, ICU-stay, hospital-stay, ICU-mortality, 90-day mortality, measurements of ischemic damage) particular in patients following transfusion.

3. Methodologic: the value of mitoPO2 in patients receiving red cell transfusion compared to markers of hypoperfusion and oxygen balance used in standard critical care: lactate, ScvO2, arterial saturation (SaO2), arterial oxygen tension (PaO2), venous oxygen tension (PvO2), cardiac index (CI)).

---

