### 7.4 Serious adverse events (SAEs)

A serious adverse event is any untoward medical occurrence or effect that

- results in death;
- is life threatening (at the time of the event);

- 
- requires hospitalisation or prolongation of existing inpatients' hospitalisation;
  - results in persistent or significant disability or incapacity;
  - Any other important medical event that did not result in any of the outcomes listed above due to medical or surgical intervention but could have, based upon appropriate judgement by the investigator.

An elective hospital admission will not be considered as a serious adverse event.

The investigator will report all SAEs to the sponsor without undue delay after obtaining knowledge of the events. Patients on the ICU are critically ill and therefore more prone to SAEs. ICU mortality in the Netherlands is approximately 8.4%. Thirty-five percent of the patients are in need for vasopressor therapy, and 46% of the patients are mechanically ventilated. Furthermore, the National Intensive Care Evaluation Report of 2015 reports that the mean ICU admittance duration is 3 days with a mean in hospital admittance duration of 13 days. Around 80% of the total ICU patients have a low APACHE IV score, and therefore a mortality chance of less than 30%. Thus, SAEs in relation to underlying disease and expected SAEs during the ICU course will not be reported.

The coordinating investigator will report the SAEs through the web portal *ToetsingOnline* to the accredited METC that approved the protocol, within 7 days of first knowledge for SAEs that result in death or are life threatening followed by a period of maximum of 8 days to complete the initial preliminary report. All other SAEs will be reported within a period of maximum 15 days after the sponsor has first knowledge of the serious adverse events.

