
Standard measurements
	
 
•Daily                     
 
•creatinin, Hb, Ht, lactate, SaO2, ScvO2, PvO2, PvCO2, PaO2, PaCO2
 
•ECG
 
•APACHE II and IV (at admission), SOFA, RIFLE
 
 
 
•Continu                     
 
•SpO2, HF, BP, CVD, UP, ICDSC, RASS, GCS
 
•inotropic therapy, vasopressor use
 
•fraction of inspired oxygen, mechanical ventilation duration and setting, renal replacement duration and settings
 
 
 

Extra determinations
	
 
•troponin
 
•CK
 

Extra measurements
	
 
•mitoPO2 at T0-T5
 
•ScvO2, SaO2, PaO2, PaCO2, PvCO2, PvO2 and lactate at T1-4
 
•Hb measurement at T3
 
•Cardiac index measurement with Vigileo II at T0 and T5
 
•Microcirculation with sublingual SDF imaging at T0 and T5
 

**Abbreviations:** BP= blood pressure; CK= creatinine kinase; CI= cardiac index; CVP= central venous pressure; ECG= electrocardiogram; FB= fluid balance; FiO2= fraction inspired oxygen; GCS= Glasgow coma scale; Hb= haemoglobin; HF= heart frequency; Ht= haematocrit; ICDSC= intensive care delirium screening checklist; ICU= intensive care unit; NYHA= New York Heart Association class; PaO2= arterial oxygen tension; PvO2= venous oxygen tension; RASS= Richmond agitation- sedation scale; RIFLE= Risk, Injury, Failure, Loss of kidney function, and End-stage kidney disease classification ; SaO2= arterial saturation; ScvO2= central venous oxygen saturation; SDF= side stream dark field imaging; SOFA= sequential organ failure assessment; SpO2= peripheral oxygen saturation; UP= urine production.

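### Section 5.4.2 names RASS, an agitation-sedation scale, as a parameter of (ischemic) brain damage in a population that includes sedated patients

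*Protocol*

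**What the plan says.** Protocol section 5.4.2 makes the value of mitoPO2 in predicting (ischemic) organ damage a secondary outcome. It introduces the list of measures with "The following parameters for organ damage (that are routinely collected) will be assessed" and then goes organ by organ: lung, heart, kidney, and finally "brain (delirium, RASS) and SOFA score". Delirium and RASS are the two brain parameters; SOFA follows outside the brain bracket. No cut-off, direction or scoring rule is given for any of them.

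Appendix 2 spells the scale out: "RASS= Richmond agitation- sedation scale".

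Objective 3 in section 2.2 is worded differently: "To describe the association between mitoPO2 and vital organ functions, as assessed by SOFA". Its list of measures ends with "Glasgow coma score, RASS, ICDSC score".

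On the population, section 8.2 gives as one ground for deferred consent "lack of decision-making capacity of the patient due to illness severity, delirium, use of sedatives, analgesics and life-sustaining treatments". The summary of changes for version 3.0 explains that consent for cardiothoracic patients was moved to before surgery because transfused patients who were still sedated had been missed. The exclusion criteria in section 3.2 do not mention sedation. Section 5.3.2 has RASS, ICDSC, SOFA and the coma scale collected daily from the patient record.

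**The concern.** An outcome parameter should measure the construct it is listed under. Here the construct is brain damage, possibly ischemic. A scale of agitation and sedation responds to sedatives whether or not the brain is injured, and these patients may be receiving sedatives around the time of transfusion.

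Three consequences follow:

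- **Misclassification.** Low RASS values in uninjured, sedated patients look the same as low values caused by brain injury.
- **Two-sided scale.** Agitation and sedation run in opposite directions from a calm, alert state. A single regression slope on RASS has no clear meaning as more or less damage.
- **Confounding.** If sedation, or the reason for it, is related to skin mitoPO2, an association can appear or be masked for reasons that have nothing to do with brain injury.

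The study is meant to decide whether mitoPO2 deserves a further diagnostic study, and section 1 hypothesises that it predicts organ dysfunction early. A brain result built on RASS could mislead that judgement in either direction.

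**Working it through.** The protocol states no figure on this point, so there is nothing to reproduce. The finding rests on setting the sections side by side.

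1. **Construct.** Section 5.4.2 places RASS under brain, among parameters of organ damage that mitoPO2 is to predict.
2. **Instrument.** Appendix 2 defines RASS as a scale of agitation and sedation.
3. **Population.** Section 8.2 and the version 3.0 change log show that sedated patients are recruited, and section 3.2 does not exclude them.
4. **Separation.** Nothing in sections 2.2, 5.3.2, 5.4.2 or 6.2 separates sedative effect from injury in the RASS outcome. The measurement log in section 4 names skin temperature, vasopressors and nurse actions, but not sedatives.

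Steps 1 to 3 establish the mismatch. Step 4 only shows that nothing elsewhere in the protocol repairs it.

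**Illustration of dilution.** From the protocol: N = 189 (section 6.1, before allowance for drop-out). The upper sedated share borrows the general Dutch ICU figure in section 7.4, "46% of the patients are mechanically ventilated", which is only a rough stand-in for sedation. Everything else is assumed: true brain injury p = 10%; true c-statistic 0.75; a share s of uninjured patients sedated and counted as injured; all truly injured patients counted as injured; sedation unrelated to mitoPO2.

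- False positives = N(1 − p)s
- True cases = Np = 189 × 0.10 ≈ 19
- True share of all counted cases = p / (p + (1 − p)s)
- Observed c = 0.5 + (0.75 − 0.5) × true share

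| s | False positives | True share | Observed c |
|---|---|---|---|
| 10% | 189 × 0.90 × 0.10 ≈ 17 | 0.10/0.190 = 0.53 | 0.63 |
| 20% | 189 × 0.90 × 0.20 ≈ 34 | 0.10/0.280 = 0.36 | 0.59 |
| 30% | 189 × 0.90 × 0.30 ≈ 51 | 0.10/0.370 = 0.27 | 0.57 |
| 46% | 189 × 0.90 × 0.46 ≈ 78 | 0.10/0.514 = 0.19 | 0.55 |

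Varying p from 5% to 20% over the same values of s gives a range from 0.53 (p = 5%, s = 46%: true share 0.05/0.487 = 0.10) to 0.68 (p = 20%, s = 10%: true share 0.20/0.280 = 0.71).

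The c-statistic is used because section 6.2 plans ROC analysis. The protocol does not say that RASS will be dichotomised in this way. If sedation is related to mitoPO2, the dilution formula no longer applies and the bias may go either way; the documents give no figure for that relation.

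**The case against.** The strongest reply is that section 5.4.2 only lists parameters to be assessed. How sedated days are scored, which days count for delirium, and which covariates enter the models are matters for an analysis plan. Section 9.6 refers to such a plan, and it is not to hand. Section 6.2 already foresees multivariable models. The scores come from routine ICU records, where local practice may already deal with sedation. Delirium stands beside RASS as a second brain parameter.

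Much of this stands. The handling of Glasgow coma score and SOFA on sedated days may well be settled elsewhere, and its absence here is not a defect. What does not fall away is the choice of parameter. The protocol states that RASS represents organ damage in the brain. An analysis plan could limit the harm, but only by departing from section 5.4.2.

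A reader might go further and infer that sedated patients are counted as the worst brain outcome, or that Glasgow coma score and SOFA are also scored as brain damage. The documents do not support either reading. There is no ranking, cut-off or worst category anywhere. Objective 3 treats coma score and SOFA as measures of organ function, section 5.4.2 puts SOFA outside the brain item and omits the coma score, and the protocol does not spell out what SOFA contains. Nor does it say how many patients are sedated: section 8.2 lists sedatives as one ground among several, without a frequency.

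**Conclusion.** The point holds for RASS. Section 5.4.2 fixes a sedation scale as a marker of (ischemic) brain damage in a population that includes sedated patients, so a mitoPO2–RASS association is not interpretable as an association with brain injury.

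The severity is minor. One parameter of one secondary outcome is affected; the primary endpoint in section 5.4.1, the sample size in section 6.1, and the lung, heart and kidney parameters are untouched. The size cannot be derived from the documents. The fall in the c-statistic from 0.75 to between 0.55 and 0.63 rests on assumed injury and sedation rates and on a coding rule that the protocol does not state, so it shows only what such a rule would do.

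**What to change.** In section 5.4.2, remove RASS from the organ-damage parameters. Keep the score, which is already collected, in two roles: as a covariate for level of sedation, and as the gate that decides whether delirium can be assessed on a given day. Analyse delirium (ICDSC) on assessable days only, with deep sedation or coma reported as a separate category.

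Where Glasgow coma score or SOFA is related to mitoPO2 under objective 3, add a sensitivity analysis that omits the neurological part on sedated days.

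The cost is a change of wording; RASS needs no new data collection. The downside is fewer assessable delirium days, and so less precision for that parameter.
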